1. GLOSSARY OF ABBREVIATIONS

Abbreviation	Description
AD	Alzheimer's Disease
ADAS-cog14	Alzheimer's Disease Assessment Scale cognitive subscale
ADCS-MCI-ADL	Alzheimer's Disease Cooperative Study/Activities of Daily Living scale adapted for MCI patients
AE	Adverse Event
ALAT	Alanine Aminotransferase
ANCOVA	Analysis of Covariance
ASAT	Aspartate Aminotransferase
ATC	Anatomical Therapeutic Chemical
BDRM	Blinded Data Review Meeting
BMI	Body Mass Index
CDR	Clinical Dementia Rating
CFT	Category Fluency Test
CGIC	Clinical Global Impression of Change
CI	Confidence Interval
cNTB	computerized Neuropsychological Test Battery
COWAT	Controlled Oral Word Association Test
CRF	Case Report Form
CTCAE	Common Terminology Criteria for Adverse Events
CV	Coefficient of Variation
DBL	Data Base Lock
DET	Detection
DMC	Data Monitoring Committee
DMP	Data Management Plan
ECG	Electrocardiogram
FAS	Full Analysis Set
FDA	Food and Drug Administration
GCP	Good Clinical Practice

Abbreviation	Description
GGT	Gamma-Glutamyltransferase
ICH	International Council on Harmonization
IDN	Identification
ISLT	International Shopping List Test
IVRS	Interactive Voice Randomization System
IWRS	Interactive Web Randomization System
LOTE	Lack of Therapeutic Efficacy
Max	Maximum
MCH	Mean Corpuscular Hemoglobin
MCI	Mild Cognitive Impairment
MCMC	Markov Chain Monte Carlo
MCV	Mean Corpuscular Volume
MedDRA	Medical Dictionary for Regulatory Activities
Min	Minimum
MMRM	Mixed-effects Maximum likelihood Repeated Measures
MMSE	Mini Mental State Examination
N/A	Not Applicable
NA	Not Applicable
NCI	National Cancer Institute
NPI	Neuropsychiatric Inventory
OBK	One Back Card
OCL	One Card Learning
PPS	Per Protocol Set
PSQI	Pittsburgh Sleep Quality Index
PT	Preferred Term
QC	Quality Control
QTc	Corrected QT Interval
SAE	Serious Adverse Event
SAP	Statistical Analysis Plan

Abbreviation	Description
SD	Standard Deviation
SHBG	Sex Hormone Binding Globulin
Sheehan-STS	Sheehan Suicidality Tracking Scale
SE	Standard Error
SI	Standard International System of Units
SOC	System Organ Class
SOP	Standard Operating Procedure
SS	Safety Analysis Set
STS	Suicidality Tracking Scale
TEAE	Treatment Emergent Adverse Event
TLF	Table, Listing and Figure
VAS	Visual Analogue Scale
WHO	World Health Organization

2. PURPOSE

The purpose of this statistical analysis plan (SAP) is to ensure that the data listings, summary tables and figures which will be produced, and the statistical methodologies that will be used, are complete and appropriate to allow valid conclusions regarding the study objectives.

2.1. RESPONSIBILITIES

INC Research will perform the statistical analyses and are responsible for the production and quality control of all tables, figures and listings.

2.2. TIMINGS OF ANALYSES

The primary analysis of safety and efficacy and/or pharmacokinetics is planned after all subjects complete the final study visit or terminate early from the study, and database is locked after all data related edits and queries are resolved.

3. STUDY OBJECTIVES

3.1. PRIMARY OBJECTIVE

The primary objective of the study is to compare the effect of piromelatine (5, 20, and 50 mg) to that of placebo in the change from baseline in global composite score of the computerized Neuropsychological Test Battery (cNTB) after 26 weeks of double-blind treatment.

The global composite score includes the computerized International Shopping List Test (ISLT; immediate and delayed recall), One Card Learning (OCL), Identification (IDN), Detection (DET), One Back Card (OBK), and the paper-based Controlled Oral Word Association Test (COWAT) and Category Fluency Test (CFT).

3.2. SECONDARY OBJECTIVES

The key secondary objectives are:

1. To compare the effect of piromelatine (5, 20, and 50 mg) to that of placebo on global impression assessed by the Clinical Global Impression of Change (CGIC) after 26 weeks of double-blind treatment.
2. To compare the effect of piromelatine (5, 20, and 50 mg) to that of placebo in the Alzheimer's Disease Cooperative Study/Activities of Daily Living scale adapted for MCI patients (ADCS-MCI-ADL) at Weeks 13 and 26 and over 26 weeks of double-blind treatment.

The other secondary objectives are:

1. To compare the effect of piromelatine (5, 20, and 50 mg) to that of placebo in Alzheimer's Disease Assessment Scale cognitive subscale (ADAS-cog14) at Weeks 13 and 26 and over 26 weeks of double-blind treatment.
2. To compare the effect of piromelatine (5, 20, and 50 mg) to that of placebo in the change from baseline in global composite score of the cNTB at Weeks 4 and 13 and over 26 weeks of double-blind treatment.

3.3. EXPLORATORY OBJECTIVES

The exploratory objectives are:

1. To compare the effect of piromelatine (5, 20, and 50 mg) to that of placebo on the episodic memory domain* composite score of the cNTB at Weeks 4, 13, and 26 and over 26 weeks of double-blind treatment.

* episodic domain tests: ISLT (immediate and delayed recall) and OCL

2. To compare the effect of piromelatine (5, 20, and 50 mg) to that of placebo on the attention domain* composite score of the cNTB at Weeks 4, 13, and 26 and over 26 weeks of double-blind treatment.

* Attention domain tests: IDN and DET

3. To compare the effect of piromelatine (5, 20, and 50 mg) to that of placebo on the executive function* composite score of the cNTB at Weeks 4, 13, and 26 and over 26 weeks of double-blind treatment.

* Executive function domain tests: OBK, COWAT and CFT.

4. To compare the safety and tolerability of piromelatine (5, 20, and 50 mg) to that of placebo.
5. To compare the effect of piromelatine (5, 20, and 50 mg) to that of placebo on cognitive aspects of mental function assessed by the Mini Mental State Examination (MMSE) after 2 weeks of run-in single-blind placebo and 26 weeks of double-blind treatment.
6. To compare the effect of piromelatine (5, 20, and 50 mg) to that of placebo on individual cNTB test scores (ISLT immediate and delayed recall, OCL, IDN, DET, OBK, COWAT, and CFT) at Weeks 4, 13, and 26 and over 26 weeks of double-blind treatment.
7. To compare the effect of piromelatine (5, 20, and 50 mg) to that of placebo on the change from baseline in behavioral signs and symptoms assessed by the Neuropsychiatric Inventory (NPI) Scale after 26 weeks of double-blind treatment.
8. To compare the effect of piromelatine (5, 20, and 50 mg) to that of placebo on sleep variables derived from the Pittsburgh Sleep Quality Index (PSQI) at Weeks 4, 13, and 26 and over 26 weeks of double-blind treatment.
9. To compare the effect of piromelatine (5, 20, and 50 mg) to that of placebo in ADAS-cog13, ADAS-cog12, and ADAS-cog11 score at Weeks 13 and 26 and over 26 weeks of double-blind treatment.

3.4. BRIEF DESCRIPTION

This is a Phase 2, double-blind, parallel group, placebo-controlled, dose ranging safety and efficacy study of piromelatine in patients with mild dementia due to Alzheimer's disease (AD).

During the double-blind period, patients will be enrolled in a 1.2:1:1:1 randomization ratio to the 4 trial arms (placebo [1.2], and the equal piromelatine treatment arms 5,

20, and 50 mg [1:1:1]). Intermediate visits will be carried out at 4 weeks (Visit 3) and 13 weeks (Visit 4) after randomization.

Figure 1: Overall Study Design

Period	Screening	Single-blind Run-in		Double-blind Treatment			Follow-up Phone call
		Run-in	Randomization				
Week		-2	0	4	13	26	28
Visit	1		2	3	4	5	
Treatment		Placebo		Piromelatine 5, 20, or 50 mg or Placebo			N/A

Each patient will undergo a 2-week, single blind run-in period and a 26-week, randomized, double-blind treatment period, for a total of 28 weeks. Two weeks after last dosing of study medication, the patient will receive a follow-up phone call. The duration of the study is expected to be approximately 40 months from first patient screened to final patient completing the randomized treatment.

3.5. SUBJECT SELECTION

Male and female patients between the ages of 60 and 85 (inclusive) with mild AD.

3.5.1. Inclusion Criteria

The inclusion criteria are defined in Section 11.1.2 of the protocol.

3.5.2. Exclusion Criteria

The exclusion criteria are defined in Section 11.1.3 of the protocol.

3.6. DETERMINATION OF SAMPLE SIZE

Eligible patients will be enrolled equally in a 1.2:1:1:1 randomization ratio to the 4 trial arms (placebo [1.2] and the equal piromelatine treatment arms 5 mg, 20 mg, and 50 mg [1:1:1]). Assuming an effect size between treatment dose and placebo of 0.35 over 26 weeks, a significant level (α) of 0.05 for one-sided test, and power of 80%, a sample size

of 115 patients for the placebo arm and 95 for each of the 3 piromelatine arms is calculated. Assuming a 50% screen failure rate and allowing for 15% patient withdrawal, 920 patients should be screened in order to randomly assign 460 patients, of whom it is expected 400 will complete the study. Enrollment will end on November 30th 2018.

3.7. TREATMENT ASSIGNMENT AND BLINDING

Patients will be assigned a patient number once written informed consent has been obtained. The randomization list will be generated using a computer-based system and randomization will be performed using an interactive web response system (IWRS). Patients will be randomized, with a ratio of 1.2:1:1:1:1 to each treatment group after successful completion of the single-blind run-in period.

The lead statistician will create a dummy randomization and will be used to provide the dry run of Table, Figure and Listing (TFL) outputs before database lock. An independent unblinded statistician, who will not communicate with the sponsor or other interested party, will create the actual randomization. This will be stored in a restricted folder where only the unblinded statistician will have access to.

Unblinding will occur after database lock. The lead statistician will receive the unblinded randomization list from the unblinded team and rerun all the TFL outputs using this list.

3.8. ADMINISTRATION OF STUDY MEDICATION

Piromelatine will be administered orally, once daily, after a meal, before habitual bedtime, preferably between 2100h and 2300h.

3.9. STUDY PROCEDURES AND FLOWCHART

The schedule of assessments can be found in table 10.1 of the protocol.

4. ENDPOINTS

4.1. PRIMARY EFFICACY ENDPOINT

The primary efficacy endpoint is the cNTB global composite score (ISLT immediate and delayed recall, OCL, IDN, DET, OBK, COWAT and CFT) over 26 weeks of double blind treatment.

4.2. SECONDARY EFFICACY ENDPOINTS

Efficacy will be further assessed based on the following secondary variables:

- CGIC at Weeks 13 and 26 and over 26 weeks of double-blind treatment;
- ADCS-MCI-ADL at Weeks 13 and 26 and over 26 weeks of double blind treatment;
- ADAS-cog14 at Weeks 13 and 26 and over 26 weeks of double-blind treatment;
- cNTB global composite score (ISLT, ISLT-delayed, OCL, IDN, DET, OBK, COWAT, and CFT) over 4 and 13 weeks of double blind treatment.

4.3. EXPLORATORY EFFICACY ENDPOINTS

Efficacy will be further assessed based on the following exploratory variables:

- cNTB episodic memory domain composite score (ISLT, ISLT-delayed, and OCL) at Weeks 4, 13 and 26 and over 26 weeks of double blind treatment;
- cNTB attention domain composite score (IDN and DET) at Weeks 4, 13 and 26 and over 26 weeks of double blind treatment;
- cNTB executive function composite score (OBK, COWAT and CFT) at Weeks 4, 13 and 26 and over 26 weeks of double blind treatment.
- MMSE after 2 weeks of run-in single-blind placebo and 26 weeks of double-blind treatment;
- Individual cNTB test scores at Weeks 4, 13, and 26 and over 26 weeks of double-blind treatment;
- NPI scale after 26 weeks of double-blind treatment;
- PSQI (global score and individual components) at Weeks 4, 13, and 26 and over 26 weeks of double-blind treatment;

- ADAS-cog13, ADAS-cog12, and ADAS-cog11 scores at Weeks 13 and 26 and over 26 weeks of double-blind treatment;
- All of the above primary and secondary cNTB composite global score analyses, without the paper-based CFT and COWAT in the executive function domain;
- All of the above primary and secondary analyses comparing placebo with the combined 20 mg and 50 mg piromelatine treatment group;
- All the above primary and secondary efficacy endpoints separated for ApoE4 carriers and non-carriers (see [Section 6.6](#));
- All the above primary and secondary efficacy endpoints separated for insomnia and non-insomnia patients (see [Section 6.6](#));
- All the above primary and secondary efficacy endpoints separated for naïve patients and patients taking AD medications at baseline (see [Section 6.6](#)).

4.4. SAFETY ENDPOINTS

The following variables will be collected for assessment of safety:

- Adverse events (including Serious Adverse Events [SAEs]);
- Physical examination;
- Vital signs;
- Concomitant medications;
- Laboratory parameters (hematology, biochemistry [including sex hormones], and urinalysis);
- Electrocardiograms (ECG);
- Sheehan Suicidality Tracking Scale (Sheehan-STS).

5. ANALYSIS SETS

All the primary, secondary and exploratory efficacy endpoints will be analyzed using the full analysis set. The per protocol set will also be used for the analysis of the primary and secondary efficacy endpoints. Safety and tolerability will be analyzed using the safety analysis set.

5.1. SCREENED SET

The screened set will include all patients screened who have given written informed consent. Unless specified otherwise, this set will be used for the listing and summarization of subject disposition, and for the listing of patient eligibility.

5.2. SAFETY ANALYSIS SET

The safety analysis set (SS) will include all randomized patients who were administered at least one dose of study medication. Patients will be analyzed according to treatment received. The SS will be used for all analyses of safety endpoints and for the presentation of patients in all subject listings, with the exception of disposition and eligibility.

5.3. FULL ANALYSIS SET

The full analysis set (FAS) will include all patients in the safety analysis set who have efficacy data for the primary parameter recorded for baseline and at least 1 post baseline assessment. Patients will be analyzed according to randomized treatment. The FAS will be used for all analyses of primary, secondary and exploratory efficacy endpoints (including the primary and secondary endpoints analysis of the combined 20 mg and 50 mg arm versus placebo) and for the summarization of demographics and baseline characteristics data.

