8. EFFICACY

8.1. PRIMARY EFFICACY ENDPOINT AND ANALYSIS

The primary efficacy endpoint is the change from baseline over 26 weeks of cNTB global composite score.

The global composite score of the cNTB is a composite score of the ISLT (immediate and delayed recall), OCL, IDN, DET, OBK and paper-based COWAT and CFT tests.

Calculation of scores: for each test listed above a z-score relative to study baseline will be calculated.

$$z - Score (z_{ijt}) = \frac{(x_{ijt} - \bar{x}_{1t})}{\sigma_{1t}} * Multiplicand$$

Where:

t = is the test indicator (ISLT, ISLT delayed, OCL, IDN, DET, OBK, COWAT or CFT)

i = indexes subject i

j = indexes the jth assessment for subject i (j = 1 means baseline)

x = cognitive score

x_{ijt} = subject's score for test t at the current assessment

\bar{x}_{1t} = mean performance score of the study sample for test t at baseline

σ_{1t} = standard deviation of the study sample for test t at baseline

Multiplicand equals 1 for tests for which a higher score is indicative of better cognitive performance (i.e., ISLT, ISLTR, OCL, COWAT, CFT) and -1 for tests where a lower score is indicative of better cognitive performance (i.e., IDN, DET, OBK)

Calculation of composite global score: A z-score for each test will be calculated as described above. A mean of all available z-scores for given patient in a given assessment will be calculated as the composite global score. For a given patient at a given assessment a minimum of 5 valid test scores of the tests listed above will be determined, of which at least 1 test are included from each of the domain composites as described in [Section 3.2](#).

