cNTB global composite scores and changes from baseline will be summarized (by treatment) at Visits 2, 3, 4 and 5. Change in cNTB global composite scores from baseline over 26 weeks (Visit 5) will be analyzed using a MMRM model utilizing all baseline and postbaseline data to assess any differences in treatment effects over time. The model will include fixed effects of treatment, study site, visit, and treatment by visit interaction, with baseline score, age, gender and ApoE4 as covariates, and a baseline by visit interaction. The global treatment effect estimates will be reported, with 95% confidence intervals and P values. Baseline will be the last non-missing observation at Visit 2 or before. The standard error of the change from baseline will also be included. The adjusted mean difference between treatments versus placebo will be presented along with the standard error and a 95% confidence interval.

These analyses will be performed by using PROC MIXED in SAS, and adjusted means will be obtained by using the LSMEANS statement.

An effect size calculation will be performed, where Cohen's d effect size will be calculated on the adjusted mean difference of change from baseline of treatment versus placebo. The effect size will be derived as the adjusted mean difference divided by the pooled standard deviation. The pooled within group variance (standard deviation squared) of two treatments is defined as:

$$\text{Pooled Variance} = [(n1 - 1)*\text{Var1} + (n2 - 1)*\text{Var2}] / (n1 + n2 - 2)$$

Where:

n1 = number of subjects with non-missing data for Placebo at Week 26

Var1 = variance for Placebo

n2 = number of subjects with non-missing data for active treatment at Week 26

Var2 = variance for active treatment

These analyses will be performed on the full analysis set and additionally on the per protocol set as a supportive analysis.

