A supportive efficacy analysis will be carried out using an ANCOVA method where the change in cNTB global composite scores from baseline to Week 26 will be the outcome variable and treatment group and study site will be main effects. cNTB global composite scores at baseline, age, gender, and ApoE4 will be included as covariates. The standard error of the change from baseline will also be included. Missing data (at the level of the composite score, not at the level of the individual tests) will be imputed using a pattern mixture model approach. Four patterns of missing data will be considered and imputed independently as follows:

- Pattern 1: will include patients who completed treatment on study drug (any missing data here is considered missing at random);
- Pattern 2: will include patients who discontinue treatment early due to adverse events (AEs);
- Pattern 3: will include patients who discontinue treatment early due to lack of therapeutic efficacy (LOTE);
- Pattern 4: will include patients who discontinue treatment early due to reasons other than AE event or LOTE.

The pattern mixture model methodology will be implemented using SAS procedures MI and MIANALYZE. Specifically, the following steps will be followed:

- Intermittent missing data will first be imputed using the Markov Chain Monte Carlo (MCMC) method implemented with the SAS MI procedure, which is appropriate for non-monotonic missing data.
- Data for patients who discontinue early will be multiply imputed as follows:
 - If the patient discontinues due to an AE (Pattern 2) or LOTE (Pattern 3), then missing data will be assumed to follow a distribution similar to the baseline values observed in the placebo arm of the study;
 - If the patient discontinues due to reasons other than an AE or LOTE (Pattern 4), at each time point, missing data will be assumed to follow a distribution similar to scores for patients that are still in the study and randomized to the same treatment group.
- Results of the ANCOVA on the multiply imputed data will be summarized using the SAS procedure MIANALYZE.

These analyses will be performed on the full analysis set and additionally on the per protocol set as a supportive analysis.

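### The full analysis set needs a post-baseline cNTB score, which keeps the earliest AE and lack-of-efficacy dropouts out of the pattern-mixture analysis and lets the cNTB decide who is analysed for other endpoints

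*SAP*

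**What the plan says.** SAP Section 5.3 builds the FAS from the safety set (randomised and dosed) and adds a condition: "efficacy data for the primary parameter recorded for baseline and at least 1 post baseline assessment". It then fixes the scope: "The FAS will be used for all analyses of primary, secondary and exploratory efficacy endpoints". The per-protocol set in Section 5.4 is a subset of the FAS. Section 5 names no other set for efficacy.

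On timing, Section 3.4 states: "Intermediate visits will be carried out at 4 weeks (Visit 3) and 13 weeks (Visit 4) after randomization". Section 8.1 adds: "cNTB global composite scores and changes from baseline will be summarized (by treatment) at Visits 2, 3, 4 and 5". Visit 2 is baseline, so the first scheduled post-baseline cNTB is at Week 4.

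The supportive ANCOVA in Section 8.1 imputes missing composite scores under four patterns: treatment completers, stopping for an adverse event (Pattern 2), stopping for lack of therapeutic efficacy (Pattern 3), and stopping for any other reason (Pattern 4). For Patterns 2 and 3, "missing data will be assumed to follow a distribution similar to the baseline values observed in the placebo arm of the study". For Pattern 4 the reference is patients of the same arm who are still in the study. No pattern is limited to patients who already have a post-baseline score. The analysis is assigned to the FAS and, as support, to the per-protocol set.

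**The concern.** The pattern-mixture ANCOVA is the plan's one efficacy analysis that treats dropout for adverse events or lack of efficacy differently from other missing data. The set it runs on is defined by an event after randomisation, the recording of a post-baseline cNTB. A patient who stops for an adverse event in week 2 with no such record belongs to Pattern 2 by definition but cannot reach it. For dropout that early, the supportive analysis has the same gap as the primary MMRM, so it adds nothing on whether the result is sensitive to it. If early stopping differs between doses, that is where a sensitivity analysis would be wanted.

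The same entry condition governs endpoints measured by other instruments. CGIC, ADCS-MCI-ADL and ADAS-cog14 have their own assessments at Weeks 13 and 26 (Section 4.2). MMSE and NPI are tested only through the pattern-mixture ANCOVA (Sections 8.3.4 and 8.3.6). A patient with data on one of these but no post-baseline cNTB is left out of an endpoint for which a value exists.

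**Working it through.** **1. Follow one patient through the text.** Take a patient who is randomised, dosed, has a baseline cNTB, and stops for an adverse event before Week 4 with no cNTB afterwards.

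| Step | Section | Result |
|---|---|---|
| Safety set: randomised and dosed | 5.2 | in |
| FAS: post-baseline primary parameter needed | 5.3 | out |
| Per-protocol set: subset of the FAS | 5.4 | out |
| Pattern 2: stopped early for an adverse event | 8.1 | fits |
| Pattern-mixture ANCOVA: FAS and per-protocol set only | 8.1 | excluded |

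**2. Does the method need the exclusion?** The ANCOVA uses change to Week 26 as outcome, with baseline score, age, gender, ApoE4, site and treatment in the model. For Patterns 2 and 3 the imputed value comes from placebo-arm baseline scores. For Pattern 4 it comes from same-arm patients still in the study. Neither rule uses the patient's own post-baseline score, so the method can handle these patients.

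**3. Does the primary analysis need them?** The MMRM models change from baseline. A patient with no post-baseline value contributes no outcome record, so the FAS condition makes essentially no difference there.

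**4. The plan's own withdrawal figures.** Section 3.6 gives 460 randomised, 15% withdrawal and 400 completers.
- From the percentage: 0.15 × 460 = 69 withdrawals.
- From the completers: 460 − 400 = 60 withdrawals, and 60/460 = 13.0%.
- The two differ because 460 = 400 × 1.15, whereas 460 × 0.85 = 391. Both are carried forward.

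**5. Patients excluded, all reasons.** The SAP does not say when withdrawals occur. Assume a share s before the first post-baseline cNTB; the number excluded is withdrawals × s.
- s = 20%, 60 withdrawals: 0.20 × 60 = 12, and 12/460 = 2.6%.
- s = 40%, 69 withdrawals: 0.40 × 69 = 27.6, about 28, and 27.6/460 = 6.0%.
- Wider range on 69 withdrawals: 10% gives 6.9 (1.5%) and 50% gives 34.5 (7.5%).

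**6. Of these, adverse-event or lack-of-efficacy cases.** Assume 25% to 50% of those excluded.
- Main range: 0.25 × 12 = 3, to 0.50 × 27.6 = 13.8, so about 3 to 14 patients.
- Wider range: 0.25 × 6.9 = 1.7, to 0.50 × 34.5 = 17.25, so about 2 to 17.

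**7. Possible effect on the estimate.** An active arm has 460/4.2, about 110 patients. Take the upper figure of 17 and suppose these patients have no benefit, against the planned effect of 0.35.
- Spread evenly, about 4 per arm: 0.35 × 4/110 = 0.013 SD of attenuation.
- All in one active arm: 0.35 × 17/110 = 0.054 SD.

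**The case against.** The strongest reply is that the consequence is small and the schedule is only partly visible.

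- **Early termination.** A reader might infer that these patients can never enter the analysis. The SAP leaves the assessment schedule to the protocol (Section 3.9). It mentions an early termination visit for ECG and physical examination (Sections 9.6 and 9.7) and a premature discontinuation visit for laboratory tests (Section 9.4). The list of visits at which the cNTB is summarised does not rule out collection at early termination. If the protocol collects it there, some early dropouts qualify. This stands.
- **Robustness.** A reader might infer that the supportive analysis cannot speak to robustness at all. That is too strong. Adverse-event and lack-of-efficacy dropouts after a Week 4 cNTB, over the remaining 22 of 26 weeks, are imputed under Patterns 2 and 3. Nor does the SAP show that the earliest withdrawals are the most treatment-related.
- **Cognitive performance.** A reader might infer that patients leave the secondary endpoints because they perform badly. Section 8.1 does have a validity rule for the composite, "For a given patient at a given assessment a minimum of 5 valid test scores of the tests listed above will be determined", but Section 5.3 does not tie FAS entry to it, and the SAP does not equate poor performance with an invalid test. To be lost, a patient with Week 13 or Week 26 data must have no qualifying cNTB at any post-baseline visit. That should be rare.
- **Visibility.** The plan includes a flowchart for each analysis set (Section 7.1), a table of reasons for exclusion (Table 14.1.2.2), and adverse events leading to withdrawal on the safety set (Table 14.3.1.6). These would show an imbalance in early loss between arms. They do not show what it does to the treatment estimate.
- **Limited gain.** Pattern 4 patients are imputed from their own arm, so adding them tests little. Placebo-baseline imputation gives near-zero average change, which is not clearly a harsh test in a declining disease.

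None of this removes the mismatch between the set and the imputation. Together these points make it a modest one.

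**Conclusion.** The point holds in a limited form. As written, the SAP defines patterns for patients who stop for adverse events or lack of efficacy, and then runs the analysis on a set that leaves out those who stop before any post-baseline cNTB. The imputation does not require that exclusion. The supportive analysis is truncated at the early end; later dropouts are covered, and the primary MMRM is essentially unaffected.

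About 12 to 28 of 460 randomised patients (2.6% to 6%) would be excluded for all reasons. This rests on 60 to 69 withdrawals, an assumed 20% to 40% of them before Week 4, and no cNTB at early termination. Only some would be adverse-event or lack-of-efficacy cases: about 3 to 14 if these make up 25% to 50%, which is also assumed. The effect on the estimate would be small if they were spread evenly, and larger if they clustered in one arm.

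The loss of patients from CGIC, ADCS-MCI-ADL, ADAS-cog14, MMSE and NPI follows from the same rule. It is probably rare, and the SAP gives no basis for a number. This is a worthwhile, inexpensive improvement and does not call the primary analysis into question.

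**What to change.** Before unblinding, change the SAP in three places.

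1. Section 5.3: keep the FAS as it stands for the primary MMRM.
2. Section 8.1, and the sections that refer to it for imputation: run the pattern-mixture ANCOVA on all randomised, dosed patients with a baseline value of the endpoint, analysed by randomised arm. The per-protocol version can stay as support.
3. Sections 5 and 5.3: for each non-cNTB endpoint, define inclusion by data on that endpoint and not on the cNTB. CGIC has no baseline score (Section 10), so a post-baseline CGIC rating would suffice.

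It would also help to state in the SAP whether a cNTB taken at early termination counts as a post-baseline assessment.

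The cost is wording and a changed set flag; the imputation method stays the same. The downside is a few more imputed values in a supportive analysis and slightly different patient numbers from one endpoint to the next, which table footnotes can explain.
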